4.2 Recruitment Plan

EAE is an extremely rare disorder. A maximum of 12 intention-to-treat subjects with EAE will be enrolled with a ceiling of 15 patients for subjects that drop out prior to receiving the first dose. Subjects who are withdrawn prior to receiving mepolizumab will be replaced. The anticipated recruitment period will be 2 years. Subjects will be recruited from those already enrolled on NIH protocol 94-I-0079 (“Eosinophil activation and function in parasitic infections and other conditions with increased tissue or blood eosinophilia in humans”). The NIH is a major referral center for HES, with >200 patients actively followed on protocol 94-I-0079, of which 12 are known to have EAE, and 1-2 new patients referred for evaluation of eosinophilia weekly.

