15.1 Study Hypotheses, Endpoint and Sample Size Justification

This is a pilot study designed as proof of principle, and the small sample size is dictated both by our ability to recruit sufficient numbers of patients in this rare disease and the complexity of the study design.

First, based on the fact that there are n=12 subjects already in the natural history protocol, we expect to be able to get n=5 subjects to participate in this study.

For the primary endpoint of change in maximum daily AE score (DAES), we use a quasi-Poisson model to estimate the average percent reduction after treatment compared to pre-treatment. This model accounts for within-person correlation of

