the repeated maximum DAES by allowing a different (fixed) person effect for each person, and it also allows overdispersion from the Poisson model. Because of the small sample sizes and to be conservative, we allow for overdispersion but not underdispersion and use a t-distribution for inferences. We calculate power to show that the percent reduction is greater than 0. We simulate the maximum DAES values using $n=5$ individuals measured for 4 cycles using a Poisson model with random effects for each individual (to induce within-person correlation) and additional extra-Poisson variation for each observation. Specifically, for the i^{th} individual at the j^{th} cycle, the DAES is distributed Poisson with mean: $a_i * e_{ij} * f_j$, where a_i is distributed gamma with mean 3 and variance 3 (this models the per-person average baseline maximum DAES such that 8% have values less than 1, 58% are less than 3, and 94% are less than 6), e_{ij} is distributed gamma with mean 1 and variance 0.25, and $f_j = 1$ when $j=1$ for the baseline cycle and $f_j = 1-(r/100)$ for the cycles after treatment, where r is the percent reduction. We first simulate 10,000 data sets under the null hypothesis of 0% reduction. The simulated the type I error rate for the two-sided test is 4.9% (close to the nominal 5%); however, the one-sided type I error rate is slightly inflated at 3.4% (for a nominal 2.5%). This slight inflation is due to the small sample size and because of this, we will make two-sided inferences. Next we simulate 10,000 data sets with 87.5% reduction and show that we have over 91% power to show a significant effect at the two-sided 5% level. For the analysis we will present two-sided 95% confidence intervals which can show larger effects than just the difference from 0. For example, the simulations show that with an 87.5% reduction we have 80% power to show that the percent reduction is at least 30% (i.e., 80% of the simulated 95% confidence intervals show percent reductions of at least 30%).

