15.2 Description of the Analyses

- **Safety Analysis:** All safety data will be summarized with descriptive statistics (number of subjects [N], mean, standard deviation, median, minimum, and maximum) for continuous variables, and frequency and percentage for discrete variables. The safety summary will include AEs, SAEs, and clinical laboratory data.
- **Efficacy Analysis (change in symptoms):** For the primary endpoint we will use the quasi-Poisson model as described in section 15.1. As a sensitivity analysis, we will model the sum of the DAES during each cycle (instead of the maximum), and perform quasi-Poisson analysis on that. We may also perform analyses on specific symptoms. For binary symptoms (present/absent), we will use a two-sided exact McNemar's test to see if there is a change in the presence of the symptom in the baseline cycle as compared to the first subsequent post-treatment cycle. For ordinal symptom data (i.e., counts of the event during a cycle), we will use a Wilcoxon signed rank tests. For continuous data we can use the methods for the percent change in peak AEC (i.e., confidence intervals based on the t-distribution of the transformed data).
- **Efficacy Analysis (peak AEC):** For the percent change in peak AEC, we will calculate tests and confidence intervals based on a one-sample t-test on the transformed responses. Specifically, we will transform the percent change in peak AEC to the log of the ratio of post-treatment peak AEC over the baseline peak AEC. Notationally, let x_i be the percent change in peak AEC for subject i , then the log of the ratio of post-treatment peak AEC over baseline peak AEC is $W_i = \log(1-[x_i/100])$. Then we will calculate the mean of the W_i and the 95% confidence interval about that mean, and back-transform the results to the percent change in peak AEC. If the resulting confidence interval is completely above 75% reduction, then this shows that, at the 2.5% one-sided level, the percent reduction is greater than 75%.

16. Protection of Human Subjects

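### Two-sided inference leaves the 3.4% false-positive rate for benefit unchanged, and type I error is not given for N = 12, where the plan's own model gives about 6.6% two-sided

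*Combined protocol and SAP*

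**What the plan says.** Section 15.2 sets the primary analysis: "For the primary endpoint we will use the quasi-Poisson model as described in section 15.1". Section 15.1 describes that analysis as a quasi-Poisson model with a fixed effect per person, overdispersion allowed but not underdispersion, and a t reference distribution.

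Section 15.1 checks the test by simulation at n=5 with four cycles (one baseline, three post-treatment). It reports:

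- null type I error of 4.9% two-sided and 3.4% one-sided (nominal 5% and 2.5%);
- power of over 91% for an 87.5% reduction;
- 80% power, for the same effect, to show a reduction of at least 30%.

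It explains the 3.4% and responds to it in one sentence: "This slight inflation is due to the small sample size and because of this, we will make two-sided inferences". It then gives the interval a role beyond the test: "For the analysis we will present two-sided 95% confidence intervals which can show larger effects than just the difference from 0".

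On sample size, section 15.1 says "we expect to be able to get n=5 subjects to participate in this study". The Protocol Summary lists N = 12, and section 4.2 says "A maximum of 12 intention-to-treat subjects with EAE will be enrolled". No type I error is given for any n other than 5.

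**The concern.** The sentence in section 15.1 treats two-sided inference as the answer to an inflated one-sided error. For a t-type test it cannot be. Both tests use the 0.975 quantile as the cut-off for a reduction, so they reject for benefit on identical data. Only the reporting changes: the benefit tail is added to a smaller harm tail and the total lands near 5%.

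The second issue is that the reassuring 4.9% belongs to one sample size. If enrolment goes from 5 towards 12, the reader has no reported error rate for the test that will be used, and the stated cause (small n) implies that things improve.

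Benefit is the direction on which this open-label single-arm study judges efficacy. The limit of the 95% interval that supports a reduction carries the same tail error.

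**Working it through.** **Inputs, all from section 15.1.** For person *i* and cycle *j*, the score is Poisson with mean a_i × e_ij × f_j. The person effect a_i is gamma with mean 3 and variance 3. The extra-Poisson term e_ij "is distributed gamma with mean 1 and variance 0.25". f = 1 at baseline and 1 − r/100 in the three later cycles.

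**Test.** With B the baseline total and P the post-treatment total over all persons:

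- log ratio = log[(P/3)/B]
- SE = √[φ(1/B + 1/P)], with φ = max(1, Pearson χ²/df)
- df = 4n − n − 1, which is 14 at n=5 (cut-off 2.145) and 35 at n=12 (cut-off 2.03)

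A data set with B = 0 or P = 0 counts as no rejection.

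**Step 1, reproduce the plan at n=5.** Null: 4.9% two-sided, made up of 3.4 to 3.5% benefit and 1.4% harm. At r = 87.5: 91% power, and 80% power to show at least 30%. All four stated figures reproduce. The plan does not name the direction of its 3.4%; the simulation shows that it is benefit.

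**Step 2, same model and test at other n (0% reduction).**

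| n | Two-sided | Benefit | Harm |
|---|---|---|---|
| 5 | 4.9% | 3.5% | 1.4% |
| 6 | 5.4% | 3.6% | 1.7% |
| 8 | 6.1% | 3.9% | 2.2% |
| 10 | 6.5% | 3.9% | 2.5% |
| 12 | 6.6% | 4.0% | 2.7% |
| 50 | 7.4% | 4.0% | 3.4% |

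Independent runs agree to about 0.1 point. Rows may not add exactly because of rounding. Excess for benefit: 3.5 − 2.5 = 1.0 point at n=5, and 4.0 − 2.5 = 1.5 points at n=12.

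**Step 3, cause.** Given a_i, the null variance is a_i + 0.25a_i², so the variance-to-mean ratio is 1 + 0.25a_i: 1.25 at a = 1, 1.75 at a = 3, 2.50 at a = 6. Quasi-Poisson uses one ratio for everyone. Averaged equally over persons the ratio is 1 + 0.25 × 3 = 1.75. In the totals B and P, which high scorers dominate, it is (3 + 0.25 × 12)/3 = 2.00, because E(a²) = 3 + 9 = 12. The standard error is therefore too small, roughly by √(2.00/1.75) = 1.07. In simulation, the SD of the log ratio against the root mean square model SE is 0.453 against 0.417 at n=5 (ratio 1.09) and 0.279 against 0.254 at n=12 (ratio 1.10). This does not fade with n.

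Two checks agree. With no extra-Poisson variation, benefit error is about 1.4% (n=5) and 2.0% (n=12). With every person at mean 3 and the same extra variation, it is about 2.8% and 3.1%.

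**Step 4, the confidence limit.** Share of trials in which the limit overstates the true reduction (nominal 2.5%):

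| True reduction | n=5 | n=12 |
|---|---|---|
| 0% | 3.5% | 3.9–4.0% |
| 30% | 3.4% | 4.1% |
| 50% | 3.1% | 4.0% |
| 70% | 2.2% | 3.5% |
| 87.5% | 0.4% | 1.8% |

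**Step 5, sensitivity.**

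- *Variances* (assumed ranges: person 1 to 6, extra-Poisson 0 to 0.5). n=5: 2.1% to 7.0% two-sided, 1.5% to 5.3% benefit. n=12: 3.3% to 9.9% two-sided, 1.9% to 6.0% benefit.
- *Cycles.* With two post-treatment cycles instead of three, benefit error is about 2.7 to 2.8% at n=5 and 3.8% at n=12. Two is plausible. Visit 4 (Day 15) to Visit 8 (Day 99) is 84 days: three 28-day cycles but only two 42-day cycles. Section 6.1 and the Table 1 notes stop daily logs after Visit 7 (Day 71), 56 days after Visit 4, while section 7.1.3 continues them to Visit 8.

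**The case against.** The strongest reply is that the plan controls two-sided error at 5%, reports 4.9%, and prints the 3.4% beside it. It never says that two-sided testing lowers the benefit tail, so nobody is misled about n=5. Much of that stands. The 4.9% is correct and the disclosure is open. A reader might infer that the plan hides an inflated error or that its simulation is wrong; the documents support neither. What remains is a rationale that does not follow, and an interval limit whose tail is the 3.4%.

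A second reply is that 12 is a maximum and section 15.1 expects 5. That is fair, and it means that 6.6% is not a forecast for the trial. But the Protocol Summary lists 12 as the sample size, and two-sided error already passes 5% at n=6.

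A third is that the size rests on unsourced inputs. This also stands. Section 15.1 gives no source for either variance, and the documents do not define how the DAES is scored; Appendix E only shows items rated 1 to 4. A bounded, underdispersed score could make the test conservative because of the dispersion floor. As an assumed example, a binomial score of 0 to 10 with mean 3 and variation between persons gives benefit error of 0.4% at n=5 and 0.6% at n=12. Other scorings could go the other way.

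Finally, a recalibrated cut-off would be tuned to those same unsourced variances and costs power for moderate effects. That is a good reason to make it optional.

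**Conclusion.** The point holds as a flaw in rationale and reporting. Two-sided inference leaves the benefit error at about 3.4 to 3.5% at n=5. Under the plan's own model it is about 4.0%, with 6.6% two-sided, at N = 12. Small sample size is not the main cause: one dispersion factor is applied where the extra-Poisson variance is quadratic in means that differ between persons.

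These figures assume the section 15.1 variances and three post-treatment cycles. The inflation disappears without extra-Poisson variation, and nearly disappears at n=5 with two cycles.

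A reader might infer that the primary test is invalid or that the 87.5% worked example fails. Neither follows. At that effect the limit is conservative (0.4% at n=5, 1.8% at n=12), and power at N = 12 is above 99.9%. The exposure is to a true effect that is null to moderate. Severity is minor to moderate for an open-label pilot.

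**What to change.** 1. In section 15.1, delete the statements that the inflation is due to small sample size and that two-sided inference answers it.
2. Restate type I error by direction, and power, at n=5, at N = 12 and at sizes between. Give the range over the assumed variances and over two or three post-treatment cycles.
3. State that, under the planning model, the nominal 95% limit supporting a reduction has a tail error of about 3.5% (n=5) to 4% (n=12) under no effect, against 2.5% nominal, and stays above nominal for reductions up to 50% (3.1% and 4.0% there).

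This costs wording and a rerun of the existing simulation.

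Optional, at the sponsor's choice: a cut-off for the reduction direction calibrated by simulation, about 2.3 under the planning model. A fixed 2.34 gives benefit error of 2.3 to 2.5% for n=5 to 12. Its power cost should be stated:

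- 87.5% reduction: 91% to 88% at n=5; still at least 99.9% at n=12.
- 50% reduction: 36% to 31% at n=5, 54% to 45–46% at n=8, 70% to 62% at n=12.

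So should the error that remains if the variances differ: with 2.34, benefit error of 0.9% to 4.1% at n=5 and 0.9% to 3.9% at n=12 over the same variance range.

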15.2 Description of the Analyses

- **Safety Analysis:** All safety data will be summarized with descriptive statistics (number of subjects [N], mean, standard deviation, median, minimum, and maximum) for continuous variables, and frequency and percentage for discrete variables. The safety summary will include AEs, SAEs, and clinical laboratory data.
- **Efficacy Analysis (change in symptoms):** For the primary endpoint we will use the quasi-Poisson model as described in section 15.1. As a sensitivity analysis, we will model the sum of the DAES during each cycle (instead of the maximum), and perform quasi-Poisson analysis on that. We may also perform analyses on specific symptoms. For binary symptoms (present/absent), we will use a two-sided exact McNemar's test to see if there is a change in the presence of the symptom in the baseline cycle as compared to the first subsequent post-treatment cycle. For ordinal symptom data (i.e., counts of the event during a cycle), we will use a Wilcoxon signed rank tests. For continuous data we can use the methods for the percent change in peak AEC (i.e., confidence intervals based on the t-distribution of the transformed data).
- **Efficacy Analysis (peak AEC):** For the percent change in peak AEC, we will calculate tests and confidence intervals based on a one-sample t-test on the transformed responses. Specifically, we will transform the percent change in peak AEC to the log of the ratio of post-treatment peak AEC over the baseline peak AEC. Notationally, let x_i be the percent change in peak AEC for subject i , then the log of the ratio of post-treatment peak AEC over baseline peak AEC is $W_i = \log(1-[x_i/100])$. Then we will calculate the mean of the W_i and the 95% confidence interval about that mean, and back-transform the results to the percent change in peak AEC. If the resulting confidence interval is completely above 75% reduction, then this shows that, at the 2.5% one-sided level, the percent reduction is greater than 75%.

16. Protection of Human Subjects

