2.1 Primary Objective

To determine the effect of mepolizumab on the number and severity of symptoms of EAE.

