Appendix D: Cycle Length Determination for 3 Patients

Appendix E: Patient Symptom Log (Daily)

The following information will be captured on an electronic version of this log through REDCap.

Name:

Instructions: Record oral temperature and write "C" for degrees Celsius or "F" for degrees Fahrenheit. Take temperature and weight around the same time each day, preferably morning.

Rate the severity of **general symptoms** experienced due to your EAE each day. If there were no symptoms on one day, check the "No Symptoms" box and leave blank all listed symptoms.

Record all **medications** taken for any of the above symptoms for each day (name, dose, number of times taken, how often taken, and reason; for example, "Ibuprofen, 200 mg, 2 tabs 4 times today for headache"). If there were no medications on a particular day, the "None" box should be checked.

Date (mm/dd)	—	—	—	—	—	—	—	—	—
Temperature (write F or °C)	—	—	—	—	—	—	—	—	—
Weight (write lbs or kg)	—	—	—	—	—	—	—	—	—
GENERAL SYMPTOMS									
NO SYMPTOMS If you have any of the symptoms below, then rate their severity from 1 to 4: 1 – mild; 2 – moderate; 3 – severe; 4 – severe and leads to doctor/ER visit or hospitalization									
Fever	—	—	—	—	—	—	—	—	—
Muscle and body aches	—	—	—	—	—	—	—	—	—
Swelling	—	—	—	—	—	—	—	—	—
Swollen lymph nodes	—	—	—	—	—	—	—	—	—
Hives	—	—	—	—	—	—	—	—	—
Pain, redness, swelling, itching, or burning at injection site (please specify)	—	—	—	—	—	—	—	—	—
Rash	—	—	—	—	—	—	—	—	—
Fatigue	—	—	—	—	—	—	—	—	—
Headache	—	—	—	—	—	—	—	—	—
Other symptoms (please describe)	—	—	—	—	—	—	—	—	—
MEDICATIONS OR OTHER EVENT									
Were you evaluated by a health professional?	NONE								
List all medications taken for any of the above symptoms, or any other event. Also list any changes in medication.	—	—	—	—	—	—	—	—	—

If you experience new symptoms or have questions, contact [name] at [contact], [contact]; or [name] at [contact], [contact]. For after hours or weekend emergencies, call the NIH page operator at [contact] to page [name].

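### The optional single-symptom tests in Section 15.2 use presence or event counts and leave out the daily 1–4 severity grade; the McNemar test can miss a symptom that becomes mild without disappearing

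*Combined protocol and SAP*

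**What the plan says.** The primary objective (Section 2.1) is "To determine the effect of mepolizumab on the number and severity of symptoms of EAE". The primary endpoint in Section 3.3.1 has the same two parts.

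Severity is collected. The daily log in Appendix E lists fever, aches, swelling, lymph nodes, hives, rash, fatigue, headache and others, with the instruction "If you have any of the symptoms below, then rate their severity from 1 to 4". A day without symptoms is ticked as such, so each symptom has in effect a 0–4 grade every day.

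The primary analysis in Section 15.2 is a quasi-Poisson model of the maximum daily score (DAES) per cycle, with the cycle sum as sensitivity analysis. Single-symptom analyses come after that and are optional. Three methods are named by type of data:

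- Present/absent: "For binary symptoms (present/absent), we will use a two-sided exact McNemar's test to see if there is a change in the presence of the symptom", comparing the baseline cycle with the first post-treatment cycle.
- Ordinal: "For ordinal symptom data (i.e., counts of the event during a cycle), we will use a Wilcoxon signed rank tests".
- Continuous: t-based intervals, as for peak eosinophil count.

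None of the three mentions the 1–4 grade. No power is stated for any single-symptom test.

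Two sample sizes appear. Section 4.2 says "A maximum of 12 intention-to-treat subjects with EAE will be enrolled"; Section 15.1 says "we expect to be able to get n=5 subjects to participate in this study".

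**The concern.** The précis asks whether eosinophils drive the angioedema and urticaria. A composite score cannot separate one feature from another; analyses by symptom can. If they are run as written, they use whether a symptom occurred, or how often, but not how bad it was. Inclusion criterion 3 requires symptoms in the cycle before screening, so common symptoms will probably be present in nearly every baseline cycle. A presence test then sees improvement only where a symptom vanishes for a whole cycle. The risk is a report of no change for a symptom that became much milder.

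**Working it through.** **1. What each test sees.** Two illustrative patients, baseline cycle against first post-treatment cycle, for one symptom:

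| Pattern | Presence (McNemar) | Days with symptom | Worst daily grade |
|---|---|---|---|
| 5 days at grade 4, then 5 days at grade 1 | no change | 5 to 5, no change | 4 to 1 |
| 10 days at grade 3, then 1 day at grade 3 | no change | 10 to 1 | 3 to 3, no change |

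The count test keeps frequency and misses a change of grade on unchanged days. The worst grade does the reverse. McNemar misses both patterns.

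**2. The smallest McNemar result that reaches 5%.** With k discordant pairs all in one direction, the exact two-sided p is 2 × 0.5^k. For k = 5 it is 0.0625; for k = 6 it is 0.031. Any pair in the other direction raises the number required. So at N = 12, fewer than six disappearances cannot be significant, whatever happens to severity in the other patients.

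**3. The plan's own figures.** The Section 15.1 model takes five "individuals measured for 4 cycles using a Poisson model with random effects for each individual": person mean gamma (mean 3, variance 3), extra variation gamma (mean 1, variance 0.25), Poisson scores, and an 87.5% reduction in three post-treatment cycles. Fitting quasi-Poisson with fixed person effects, dispersion not below 1, and t with 20 − 6 = 14 degrees of freedom gives:

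- power 91.2% (the plan: "we have over 91% power to show a significant effect at the two-sided 5% level");
- 80.1% of intervals showing at least a 30% reduction (plan: 80%);
- two-sided type I error 4.9% (plan: 4.9%).

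These reproduce, and none of them involves a single-symptom test.

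**4. Power for one symptom, with the generator borrowed.** The documents give no prevalence, severity distribution or effect for a single symptom. Assumption: the Section 15.1 generator describes one symptom's cycle score; N = 12; one baseline and one post-treatment cycle; person variance equal to the mean. Exact McNemar on score > 0 is compared with exact (permutation) signed-rank on the score, two-sided 5%, 4,000 data sets per scenario.

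| Baseline mean | Reduction | McNemar | Signed-rank | Gap (points) |
|---|---|---|---|---|
| 1.5 | 87.5% | 42% | 65% | 23 |
| 3 | 87.5% | 64% | 95% | 31 |
| 6 | 87.5% | 53% | nearly 100% | about 47 |
| 3 | 75% | 26% | 80% | 54 |

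Capping scores at 4, as for a worst daily grade, changes little: at 87.5% the pairs are 42% and 64%, 63% and 94%, 53% and 99.5%. With no effect, both tests stay below 5%. The gap is wide at mean 6 because about 96% of baseline cycles and 48% of post-treatment cycles still show the symptom.

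**5. Outside that generator.** Suppose all 12 have the symptom at baseline and each loses it with probability q. McNemar power is P(X ≥ 6) for X ~ Binomial(12, q).

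- q = 0.9: McNemar above 99.9%, signed-rank 100%. Gap about 0.
- q = 0.5: McNemar 61%, signed-rank 99.9%. Gap about 39.
- q = 0, with 70% of patients dropping one grade: McNemar 0%, signed-rank 95% in simulation. Gap about 95. As a direct check, if drops are independent and nobody worsens, the tied-rank test is significant when six or more drop, and P(Binomial(12, 0.7) ≥ 6) = 96%.

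**6. The planned count test.** Assuming a mean of 6 symptom days, Wilcoxon on counts at N = 12 has power 51%, 94% and 99.8% for reductions of 50%, 75% and 87.5%. McNemar has 0.3%, 10% and 49%. The count test has no comparable power loss when frequency falls.

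**7. At n = 5.** The smallest two-sided p for exact McNemar and for exact signed-rank alike is 2 × 0.5^5 = 0.0625. Neither can reach 5%.

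**The case against.** The strongest reply is that little depends on these tests. They are optional, carry no stated power and follow a powered composite analysis that is the plan's answer to number and severity. That stands, and it keeps the point minor. One qualification is that the documents do not define how DAES is built from the log, so whether the composite carries severity cannot be confirmed. That is a separate gap.

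A second reply is that Section 15.2 lists methods by data type and nowhere says that graded items will be dichotomised. A reader might infer that a present/absent symptom can only be a cut of a graded item. The documents do not support that: the Angioedema Activity Score in Appendix G, completed daily, opens with a genuine yes/no question on swelling, and McNemar suits it. Temperature and weight are logged daily and could be analysed under the continuous branch. What remains is that the plan names no method for the grade recorded for every symptom in Appendix E.

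Third, the count test should not be grouped with McNemar as a loss of power; item 6 of the working shows otherwise. Its only defect is that it omits severity.

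Fourth, at the five participants whom Section 15.1 expects, a graded test gains nothing in significance. That also stands. The gain applies at the planned 12.

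**Conclusion.** The point holds as a minor one. The named single-symptom tests do not use the severity grade, and the McNemar test can respond to improvement only through complete disappearance in at least six of 12 patients. This follows from the text and the exact distribution without any model.

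The size of the power gap does depend on a model that the documents do not supply. With the Section 15.1 generator borrowed for one symptom at N = 12, the gap is about 23 to 47 points at an 87.5% reduction, over baseline means 1.5 to 6. Other assumptions give about 0 (symptom abolished in nearly everyone) to about 95 (symptom persists but milder). A reader might take the 31-point middle scenario as a loss of power for the trial. It is not: it is one assumed case for an optional test, and the 91% for the primary DAES analysis does not depend on it.

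**What to change.** In Section 15.2, for the Appendix E symptoms:

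- Make the single-symptom test an exact (permutation) Wilcoxon signed-rank test on one prespecified graded summary per cycle, the worst daily grade from 0 to 4. Report the median paired change with its interval.
- Keep the Wilcoxon test on counts, which covers frequency.
- Report presence as a descriptive n/N per cycle.
- Reserve McNemar for true yes/no items, such as the opening question of the Angioedema Activity Score.

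The cost is a wording change. The grades are already collected daily in REDCap, so no visit, patient or form is added. The small downside is that a change in grade is harder to read than a proportion with the symptom, which is why the proportion stays as a descriptive line.
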